#### **4.6.2            Assessments at Baseline**

In order to be randomized and to receive double-blind treatment, participants must have no significant change in medical, psychiatric, or neurological conditions or change in medication since screening. The recommended order of assessments and rating scales is as follows:

- Clinical assessments (e.g., CDR, MMSE, and ADAS-Cog), including all those that require study partner input, should be completed before any invasive safety assessments.
- Vital sign measurements, ECGs, blood draws for clinical laboratory assessments, PK, ADA, and plasma biomarker sampling, and urine samples are recommended to be conducted following scale assessments and *all* must be performed prior to study drug administration.

The recommended order of clinical assessments/rating scales at baseline is as follows:

Participant Assessments	Study Partner Assessments
1. ADAS-Cog13	1. CDR (study partner input)
2. CDR (participant interview)	2. FAQ
10-min break (optional)	3. ADCS-ADL
3. MMSE	4. ZCI-AD
4. Coding	5. QoL-AD
5. Verbal Fluency Task	6. EQ-5D
10-min break (optional)	7. RUD-Lite
6. QoL-AD	8. NPI-Q
7. C-SSRS	

ADAS-Cog13 = Alzheimer's Disease Assessment Scale–Cognition, Subscale 13; ADCS-ADL = Alzheimer's Disease Cooperative Study-Activities of Daily Living; CDR = Clinical Dementia Rating; C-SSRS = Columbia–Suicide Severity Rating Scale; EuroQoL-Five Dimensions; FAQ = Functional Activities Questionnaire; MMSE = Mini-Mental State Examination; NPI-Q = Neuropsychiatric Inventory–Questionnaire; QoL-AD = Quality of Life–Alzheimer's Disease; RUD-Lite = Resource Utilization in Dementia–Lite; ZCI-AD = Zarit Caregiver Interview–Alzheimer's Disease.

If assessments are split over 2 days, all safety assessments must be performed on the same day as the study drug administration.

#### **4.6.3 Assessments during the Double-Blind Treatment Period**

In the double-blind treatment period, participants will receive up to 49 (in scenario 1) or 55 (in scenario 2, if applicable) SC administrations of study drug over the course of 114 or 126 (if applicable) weeks, respectively. The final on-treatment efficacy and safety assessments are scheduled 2 weeks after the last dose. Participants who have completed the double-blind treatment period at the time of the implementation of *the study extension by 12 weeks* received up to 43 doses and underwent the final efficacy and safety assessments at Week 104, 2 weeks after the last dose.

The same recommended order of clinical assessments and rating scales as above for the baseline visit should be followed (omitting those that are not conducted per the schedule of activities; see [Appendix 1](#)). *However, in exceptional circumstances, for post-randomization visits, if the caregiver, the primary rater or even the participant cannot perform these assessments as per schedule of activities, they may be performed up to 4 weeks out of window.*

Vital sign measurements, ECGs, blood draws for clinical laboratory assessments, PK, ADA, plasma biomarkers, and urine must be performed prior to study drug administration. *They are also recommended to be conducted following scale assessments.*

If assessments are split over 2 days, all safety assessments must be done on same day as the treatment administration.

On each dosing day, after all assessments prior to dosing have been completed (see the schedule of activities in [Appendix 1](#)), gantenerumab or matching placebo will be administered subcutaneously at room temperature. For the first four doses, participants should be observed for a minimum of 2 hours after dosing and then for a minimum of 1 hour after all remaining doses (i.e., Doses 5 and beyond). Participants should leave the study center after injections only if they appear to be tolerating the injections. When doses are to be administered remotely from the clinical sites, study drug administration may be performed only by qualified health care providers, as defined by local regulations, who must remain with the participants for a minimum of 1 hour after each injection and be equipped with rescue medications.

Rescue medications to treat anaphylactic and anaphylactoid reactions must be available at the site or at the dosing location for HN visits. Participants and their study partners will be alerted to watch for signs of anaphylactic and anaphylactoid reactions and to contact the study center as soon as possible if any such signs are noted.

Visits at which the participant receives study drug may take place within  $\pm 7$  days of the protocol-specified date for Q4W administration and  $\pm 3$  days of the protocol-specified date for Q2W administration per the schedule of activities in [Appendix 1](#). For Q4W injections, the recommended minimum time between doses is 3 weeks. The maximum recommended time between doses should not exceed 6 weeks. For Q2W injections, the recommendation is not to administer more than 1020 mg (i.e., 2 times 510 mg Q2W) within 28 days. Always return to initial planned schedule per randomization for subsequent visits.

All visits should be scheduled as close as possible to the exact day. It is preferred that all assessments for a visit be performed on the same day, but if necessary, assessments may be performed over more than 1 day. Preferably, all clinical scales and assessments should be performed on the same day. Study drug administration should be performed only after all assessments and rating scales for the participant have been completed.

For sites and participants for whom this is practical, visits that require only dosing, vital sign measurements, urine pregnancy test, C-SSRS assessment, and adverse event assessment may be performed at an alternate location conducted by appropriate health care professionals.

Refer to [Appendix 1](#) for the schedule of activities during the treatment period.

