**Figure 8 Overall Gantenerumab Dosing Design in the Double-Blind Treatment Period**

Q2W = every 2 weeks; Q4W = every 4 weeks; SC = subcutaneous.

For Q4W injections, a time window of  $\pm 7$  days is allowed for dosing visits. For Q4W injections, the recommended minimum time between doses is 3 weeks. The maximum recommended time between doses should not exceed 6 weeks. Once study drug is administered Q2W, the time window for dosing visits is  $\pm 3$  days. For Q2W injections, the recommendation is not to administer more than 1020 mg (i.e., 2 times 510 mg Q2W) within 28 days. Always return to the initial planned schedule per randomization for subsequent visits.

Regardless of dose, each participant will undergo up to a total of 49 dosing visits in scenario 1 or 55 dosing visits in scenario 2 (if applicable, see Section 3.3.1) in the double-blind treatment period of the study. Participants who have completed the double-blind treatment period at the time of the implementation of *the 12 week study extension*, will have undergone up to 43 dosing visits. Injections will be administered as one 0.8-mL (120-mg dose), one 1.7-mL (255-mg dose), or two 1.7-mL injections (510-mg dose) subcutaneously to the abdomen, respectively.

Placebo of identical composition (except protein) and identical volume to gantenerumab will be administered by SC injection to all participants randomized to placebo at the same frequency and using the same route of administration.

On study drug administration days that include efficacy assessments (see the schedule of activities in Appendix 1), study drug must be administered at the clinical site. Study

personnel preparing and administering study drug must not be involved with any efficacy assessments or safety evaluations.

At applicable sites, study drug may be administered by a trained nursing professional at the participant's home or another suitable location, if the participant has given written informed consent to participate in home nursing visits.

Rules for dosage modification and treatment interruption or discontinuation are provided in Section [5.1.2](#).

Any overdose or incorrect administration of study drug should be noted on the Study Drug Administration electronic Case Report Form (eCRF). Adverse events associated with an overdose or incorrect administration of study drug should be recorded on the Adverse Event eCRF.

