#### **4.6.4 Assessments during Open-Label Extension Period**

The same recommended order of clinical assessments and rating scales as in the double-blind treatment period (see [Appendix 1](#)), as well as vital sign measurements,

ECGs, blood draws for clinical laboratory assessments, PK, ADA, plasma biomarkers, and urine samples must be performed prior to study drug administration. *They are also recommended to be conducted following scale assessments.* If assessments are split over 2 days, all safety assessments must be performed on the same day as the treatment administration.

On each dosing day, after all assessments prior to dosing have been completed (see [Appendix 1](#)), gantenerumab and/or matching placebo will be administered subcutaneously at room temperature. For the first eight doses, participants should be observed for a minimum of 2 hours after dosing and then for a minimum of 1 hour after all remaining doses (i.e., doses 9 and beyond). Participants should leave the study center after injections only if they appear to be tolerating the injections. When doses are to be administered remotely from the clinical sites, study drug administration may be performed only by qualified health care providers, as defined by local regulations, who must remain with the participants for a minimum of 1 hour after each injection and be equipped with rescue medications.

Rescue medications to treat anaphylactic and anaphylactoid reactions must be available at the site or at the dosing location for HN visits. Participants and their study partners will be alerted to watch for signs of anaphylactic and anaphylactoid reactions and to contact the study center as soon as possible if any such signs are noted.

In the OLE, visits at which the participant receives study drug may take place  $\pm 3$  days of the protocol-specified date for Q2W administration per the schedule of activities in [Appendix 1](#). Always return to the initial planned schedule per randomization for subsequent visits.

For sites and participants for whom this is practical, visits that require only dosing, vital sign measurements, urine pregnancy test, C-SSRS assessment, and adverse event assessment may be performed at an alternate location conducted by appropriate health care professionals.

Refer to [Appendix 1, Table 3](#) for the schedule of activities during the OLE.

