**Appendix 1: Schedule of Activities (cont.)**

**Table 1: Week –12 to Week 32; Dose Escalation with Q4W Administration (cont.)**

Assessment/Procedure	Prescreen & Screening	Baseline	Dose Escalation Period									Unsched Visit
	Weeks – 12 to – 1	Day 1	Day 4	Wk 4	Wk 8	Wk 12	Wk 16	Wk 20	Wk 24	Wk 28	Wk 32	
Dose Number		1 a		2	3	4	5 b	6 b	7 a	8 b	9 b	
Dose level in milligrams (mg)		120		120	120	255	255	255	510	510	510	
Limited physical examination l									B			x
MRI scan m, n	x o					B			B			x
CSF and matching serum sampling m, p or PET scan m, p	x											
CDR	P&SP	P&SP							P&SP			P&SP
ADAS-Cog13		P							P			P
Verbal Fluency Task		P							P			P
Coding		P							P			P
ADCS-ADL		SP							SP			SP
FAQ		SP							SP			SP
MMSE	P f	P							P			P
EQ-5D		SP							SP			SP
QoL-AD		P&SP							P&SP			P&SP
ZCI-AD		SP							SP			SP
RUD-Lite		SP							SP			SP
NPI-Q		SP							SP			SP
C-SSRS BL/SLV		P							P			P
Vital signs q	x	B	B	B	B	B	B	B	B	B	B	x
Concomitant medications	x	x	x	x	x	x	x	x	x	x	x	x
Adverse events	x	x	x	x	x	x	x	x	x	x	x	x
Urine pregnancy test r	x	B		B	B	B	B	B	B	B	B	x
Study drug administration h, s		x		x	x	x	x	x	x	x	x	

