- q Vital signs include measurements of pulse rate and systolic and diastolic blood pressure. Blood pressure and pulse rate should be taken when the participant is at rest and should not be measured unless at least 15 minutes have elapsed since the last blood draw. The same arm should be used for all blood pressure measurements. Pulse rate will be determined and will be recorded as beats per minute. If obtained manually, the pulse rate should be counted for a minimum of 20 seconds at each assessment.
- r Females of childbearing potential (including those who have had a tubal ligation) must have a urine pregnancy test performed at the site prior to each dose administration. If a urine pregnancy test is positive, it must be confirmed by a serum pregnancy test at the central laboratory. Results are to be recorded only in the source documents.
- s Study drug administration should be performed only after all assessments/rating scales for the participant are completed (unless indicated otherwise). Study drug will be administered to participants by SC injection. Participants should be observed up to 2 hours after dosing. After the fourth injection visit, the observation time may be reduced to 1 hour. Study personnel preparing and administering study drug must not be involved with any efficacy assessments or safety evaluations.
- t Height measured at screening only.
- u A plasma biomarker sample will be obtained as soon as is practical (e.g., at an unscheduled visit) once the site becomes aware of the occurrence or worsening of ARIA-E or of the occurrence of ARIA-H meeting discontinuation criteria.
- v A plasma PK sample will be obtained as soon as is practical (e.g., at an unscheduled visit) once the site becomes aware of the occurrence or worsening of ARIA-E or of the occurrence of ARIA-H meeting discontinuation criteria.

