- h MRI must be performed at least 7 days before dosing and results must be available for review by site staff before dosing can proceed. MRI should be performed before or at least 3 days following a lumbar puncture.
- i Vital signs include measurements of pulse rate and systolic and diastolic blood pressure. Blood pressure and pulse rate should be taken when the participant is at rest and should not be measured unless at least 15 minutes have elapsed since the last blood draw. The same arm should be used for all blood pressure measurements. Pulse rate will be determined and will be recorded as beats per minute. If obtained manually, the pulse rate should be counted for a minimum of 20 seconds at each assessment.
- j Females of childbearing potential (including those who have had a tubal ligation) must have a urine pregnancy test performed at the site prior to each dose administration. If a urine pregnancy test is positive, it must be confirmed by a serum pregnancy test at the central laboratory. Results are to be recorded only in the source documents.
- k Study drug administration should be performed only after all assessments and rating scales for the participant are completed (unless indicated otherwise). Study drug will be administered to participants by subcutaneous injection (full details are provided in the pharmacy manual). Participants should be observed for up to 2 hours after dosing. After the 8th injection visit, this observation time may be reduced to 1 hour. Study personnel preparing and administering study drug must not be involved with any efficacy assessments or safety evaluations.

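### Sections 4.6.3 and 4.6.4 set a 2-hour minimum observation time after early injections, but two Appendix 1 footnotes for the same doses read as a 2-hour maximum

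*Protocol*

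**What the plan says.** The body of the protocol gives a floor. Section 4.6.3, on the double-blind period, states: "For the first four doses, participants should be observed for a minimum of 2 hours after dosing". From dose 5 onward the minimum is 1 hour. Section 4.6.4, on the OLE, states: "For the first eight doses, participants should be observed for a minimum of 2 hours after dosing". From OLE dose 9 the minimum is again 1 hour.

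The schedule of activities is worded differently. In Appendix 1 Table 1, which covers double-blind doses 1 to 9, the dosing row ("Study drug administration h, s") carries footnote s: "Participants should be observed up to 2 hours after dosing. After the fourth injection visit, the observation time may be reduced to 1 hour". In Appendix 1 Table 5, which covers OLE doses 1 to 12, the dosing row carries footnote k: "Participants should be observed for up to 2 hours after dosing. After the 8th injection visit, this observation time may be reduced to 1 hour".

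Section 4.6.4 also closes by sending the reader to Appendix 1 Table 3 for the OLE schedule. Table 3 is the double-blind Scenario 1 extension from Week 104. The OLE schedule is in Tables 5 and 6, which Section 3.1.1 cites correctly.

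**The concern.** A minimum of 2 hours and a time of up to 2 hours are opposite bounds on the same quantity, for the same doses. The instruction is operative: it decides how long a participant stays under observation after the first exposures to a subcutaneous antibody, and Section 4.6.3 requires rescue medication for anaphylactic and anaphylactoid reactions wherever a dose is given. Section 4.5 points sites to Appendix 1 for the activities at each visit, and I found no statement that the body prevails over a footnote when the two differ. A site that works from the table could therefore release someone earlier than the body allows and regard itself as compliant.

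**Working it through.** There is no figure to reproduce. The check is a comparison of wording, matched on dose number, across all six Appendix 1 tables.

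| Appendix 1 footnote | Doses covered | Footnote wording, in short | Minimum in body | Conflict? |
|---|---|---|---|---|
| Table 1, s | Double-blind 1–9 | Up to 2 h; 1 h after fourth visit | 2 h for 1–4; 1 h for 5–9 | Yes, doses 1–4 |
| Table 2, n | Double-blind 10–43 | Up to 2 h; 1 h after fourth visit | 1 h | No early dose covered |
| Table 3, n | Double-blind 44–49 | About 1 h | 1 h | No early dose covered |
| Table 4, n | Double-blind 44–55 | About 1 h | 1 h | No early dose covered |
| Table 5, k | OLE 1–12 | Up to 2 h; 1 h after eighth visit | 2 h for 1–8; 1 h for 9–12 | Yes, doses 1–8 |
| Table 6, m | OLE 13–18 | Up to 2 h; 1 h after eighth visit | 1 h | No early dose covered |

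1. Four footnotes use the up-to-2-hours wording (Tables 1, 2, 5 and 6). Tables 2 and 6 start at dose 10 and OLE dose 13, where the reduction to 1 hour already applies. That leaves two footnotes that bear on doses with a 2-hour minimum.

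2. For those doses, write t for the observation time. The body requires t ≥ 2 h. The footnote, read literally, requires t ≤ 2 h. Only t = 2 h satisfies both. Release at 90 minutes after dose 1 gives 1.5 h ≤ 2 h, which meets the footnote, and 1.5 h < 2 h, which breaches Section 4.6.3.

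3. The cut-points agree: the fourth injection in Section 4.6.3 and footnote s, the eighth in Section 4.6.4 and footnote k. The disagreement is therefore only between minimum and up to, not about which doses are early.

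4. Intended meaning: each footnote goes on to permit a reduction to 1 hour after the fourth or eighth visit. Permission to reduce makes sense only if 2 hours is the standard before that point. This supports the body's reading and points to a slip in the footnotes.

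5. Reach into the analysis: Section 5.3.5.2 defines injection reactions by onset during dosing or in the following 24 hours, whatever the on-site observation time. The SAP has no analysis that uses observation time.

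**The case against.** The best defence is that nobody would misread this. The sentence on reduction makes 2 hours the evident default, the cut-points match, participants leave the centre only if they seem to be tolerating the injection, and they and their study partners are told which signs to report. Section 5.1.1.3 describes the immunogenic risk as low. The OLE count also overstates exposure: participants previously on active drug have already been through the double-blind course, and for those previously on placebo Table 4 of the protocol gives active drug at OLE doses 1, 3, 5 and 7 only, 4 of the 8. All of this stands and keeps the severity low. It does not make the footnotes correct, because the literal text still permits what the body forbids.

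A reader might go further and infer that a home-dosing provider may leave 1 hour after an early dose. Section 4.6.3 says of remote providers "who must remain with the participants for a minimum of 1 hour after each injection", Section 4.3.2.1 gives a general permission ("At applicable sites, study drug may be administered by a trained nursing professional"), and Section 4.6.3 adds that "visits that require only dosing, vital sign measurements, urine pregnancy test, C-SSRS assessment, and adverse event assessment may be performed at an alternate location". The documents do not support that inference:

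- Section 4.5 ties home-nursing visits to specified visit days.
- Tables 1 and 5 mark visits as suitable for home administration only from double-blind dose 5 and OLE dose 9, exactly where the minimum falls to 1 hour.
- A short list of visit activities does not make a visit home-suitable. In Table 2, doses 11 and 12 involve little beyond dosing and routine checks, yet carry no home mark.
- The 2-hour sentences in Sections 4.6.3 and 4.6.4 have no limit on location. The 1-hour remote rule is a second minimum beside the first, and a 2-hour stay meets both.

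No remote-dosing conflict is therefore claimed.

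**Conclusion.** The inconsistency is in the current text and is wrong as written. It is confined to Table 1 footnote s and Table 5 footnote k, and concerns 4 double-blind doses per participant and 8 OLE dose numbers for those who enter the OLE. Severity is low. This is a point of internal consistency in a safety instruction, not a challenge to a design choice.

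The conclusion rests on a literal reading of the footnotes and on the body stating the intended rule, which the reduction clause supports. The documents give no count of participants released early, and none is assumed. They also do not say how many early doses remain to be given under Version 5, so the practical benefit of correction cannot be sized. Nothing here bears on the primary estimand, the efficacy or safety endpoints, power or type I error.

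The Table 3 cross-reference in Section 4.6.4 is also wrong, but it is clerical: Tables 5 and 6 are plainly headed as the OLE schedule, so no consequence follows.

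**What to change.** In Appendix 1 Table 1 footnote s and Table 5 footnote k:

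- replace *up to 2 hours* with *a minimum of 2 hours*;
- replace *reduced to 1 hour* with *reduced to a minimum of 1 hour*.

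As an editorial correction, change the reference at the end of Section 4.6.4 from Appendix 1 Table 3 to Tables 5 and 6. Sections 4.6.3 and 4.6.4 need no new text on observation times.

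The cost is a wording change to two footnotes and one cross-reference, carried in the next protocol amendment with the IRB/EC and regulatory steps of Section 9.6 as locally required, and a notice to sites with that amendment. No data collection, analysis or programming changes.

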#### **4.6.4 Assessments during Open-Label Extension Period**

The same recommended order of clinical assessments and rating scales as in the double-blind treatment period (see [Appendix 1](#)), as well as vital sign measurements,

ECGs, blood draws for clinical laboratory assessments, PK, ADA, plasma biomarkers, and urine samples must be performed prior to study drug administration. *They are also recommended to be conducted following scale assessments.* If assessments are split over 2 days, all safety assessments must be performed on the same day as the treatment administration.

On each dosing day, after all assessments prior to dosing have been completed (see [Appendix 1](#)), gantenerumab and/or matching placebo will be administered subcutaneously at room temperature. For the first eight doses, participants should be observed for a minimum of 2 hours after dosing and then for a minimum of 1 hour after all remaining doses (i.e., doses 9 and beyond). Participants should leave the study center after injections only if they appear to be tolerating the injections. When doses are to be administered remotely from the clinical sites, study drug administration may be performed only by qualified health care providers, as defined by local regulations, who must remain with the participants for a minimum of 1 hour after each injection and be equipped with rescue medications.

Rescue medications to treat anaphylactic and anaphylactoid reactions must be available at the site or at the dosing location for HN visits. Participants and their study partners will be alerted to watch for signs of anaphylactic and anaphylactoid reactions and to contact the study center as soon as possible if any such signs are noted.

In the OLE, visits at which the participant receives study drug may take place  $\pm 3$  days of the protocol-specified date for Q2W administration per the schedule of activities in [Appendix 1](#). Always return to the initial planned schedule per randomization for subsequent visits.

For sites and participants for whom this is practical, visits that require only dosing, vital sign measurements, urine pregnancy test, C-SSRS assessment, and adverse event assessment may be performed at an alternate location conducted by appropriate health care professionals.

Refer to [Appendix 1, Table 3](#) for the schedule of activities during the OLE.

